6.3.6 Sub-study additional visits

At select sites, study subjects will also participate in a clinical laboratory sub-study. All subjects enrolled at these sites will be asked to come for three additional visits (denoted A1, A2, A3 in Appendix 2 Schedule of Events) beyond those required for the main study and to provide 4 additional blood samples, at V1 (Study Day 0) and at A1, A2 and A3, on Study Day 7 (-3/+7 days), Study Day 35 (-3/+7 days) and Study Day 175 (-3/+7 days), respectively. These blood samples will be used to investigate and compare clinical laboratory parameters (hematology, biochemistry) following vaccination with Sci-B-Vac[™] and Engerix-B[®].

Subjects recruited from the clinical laboratory sub-study to participate in the optional sub-study of the cell-mediated immune response, will be asked to provide an additional blood sample on Study Day 0 (Visit 1) and at A1, A2 and A3 on Study Day 7 (- 3/+7 days) and Study Day 35 (-3/+7 days) and Study Day 175 (-3/+7 days) to investigate and compare cell-mediated immune response following vaccination with either Sci-B-Vac[™] or Engerix-B[®].

6.3.7 End of study visit

The end of study visit will be performed on Study Day 336 (+/-14 days) or earlier in case of withdrawal.

- Physical/History-directed physical examination.
- Blood samples for measurement of anti-HBs, anti pre-S1, and anti pre-S2 levels and characteristics will be taken.
- SAE, AE requiring medical attention and the use of concomitant medications will be recorded in the eCRF
- In case of withdrawal: reason for withdrawal will be documented in the eCRF
- Subject will be advised that the study center staff may need to contact them in case new information, such as lack of seroprotection (anti-HBs levels <10 mIU/mL), becomes available.

7 ASSESSMENT OF SAFETY

7.1 Specification of safety parameters

7.1.1 Adverse Events

An Adverse Event (AE) is any untoward medical occurrence in a subject or clinical investigation subject administered a pharmaceutical product, which does not necessarily have to have a causal relationship with this treatment.

An AE can therefore be:

- Any unfavorable and unintended sign (including an abnormal laboratory finding);
- Symptom or disease temporally associated with the use of a medicinal product, whether or not considered related to the medicinal product;
- Preexisting symptoms or conditions which worsen during a study.

7.1.2 Serious Adverse Events

A Serious Adverse Event (SAE):

- Results in death
- Is life threatening

Note: The term 'life-threatening' in the definition of 'serious' refers to an event in which the subject was at risk of death at the time of the event. It does not refer to an event, which hypothetically might have caused death, had it been more severe.

• Requires subject hospitalization or prolongation of existing hospitalization

Note: In general, hospitalization signifies that the subject has been admitted at the hospital or emergency ward for observation and/or treatment that would not have been appropriate in the physician's office or in an out-patient setting. Hospitalizations for routine procedures and investigations are not considered a SAE in this protocol.

• Results in persistent or significant disability/incapacity

Note: The term disability means a substantial disruption of a person's ability to conduct normal life functions. This definition is not intended to include experiences of relatively minor medical significance such as uncomplicated headache, nausea, vomiting, diarrhea, influenza like illness, and accidental trauma (e.g., sprained ankle) which may interfere or prevent everyday life functions but do not constitute a substantial disruption.

- Is a congenital anomaly/ birth defect
- Is another medically important event

Note: Important medical events that may not result in death, be life-threatening, or require hospitalization may be considered serious when, based upon appropriate medical judgment, they may jeopardize the subject or subject and may require medical or surgical intervention to prevent one of the outcomes listed in this definition. Should the investigator feel that an adverse event may jeopardize the subject or may require intervention to prevent more serious outcomes, then the adverse event should be treated as serious.

7.1.3 Preexisting conditions

In this trial, a preexisting condition (i.e., a disorder present before the adverse event reporting period started) should not be reported as an adverse event unless the condition worsens during the adverse event reporting period.

Anticipated day-to-day fluctuations of pre-existing disease(s) or condition(s) present or detected at the start of the study that do not worsen are not considered as AE.

7.1.4 Procedures

Diagnostic and therapeutic noninvasive and invasive procedures, such as surgery, should not be reported as AE. However, the medical condition for which the procedure was performed should be reported if it meets the definition of an AE. For example, an acute appendicitis that begins during the adverse event reporting period should be reported as an adverse event and the resulting appendectomy noted under Comments.

7.1.5 Laboratory test abnormalities and other abnormal assessments

In subjects participating in the clinical laboratory sub-study, laboratory test value abnormalities and other abnormal assessment will be reported as AE, if they satisfy one or more of the following conditions for clinical significance:

- accompanied by clinical symptoms
- requiring a change in concomitant therapy (e.g. addition of, interruption of, discontinuation of, or any other change in a concomitant medication, therapy or treatment).
- In absence of clinical symptoms or change in concomitant therapy if the investigator judges it to be clinically significant
- Clinically significant abnormal laboratory findings and other abnormal assessment present at baseline and significantly worsening following the start of the study

The investigator will exercise his or her medical and scientific judgment in deciding whether an abnormal laboratory finding is clinically significant.

7.1.6 Grading of AEs

7.1.6.1 Unsolicited Adverse Events

These adverse event will be graded according to the severity scale in Table 1.

Table 1: Unsolicited AEs severity scale

Grade 1 (Mild)	No interference with daily activity
Grade 2 (Moderate)	Some interference with daily activity but not requiring medical intervention
Grade 3 (Severe)	Prevents daily activity and requires medical intervention
Grade 4 (Potentially life threatening)	Requiring Emergency Room (ER) visit or hospitalization

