7.2.1 AEs

All new AE or abnormal laboratory test values considered as clinically significant, expected or unexpected related or unrelated experienced after the subject received the study treatment should be recorded in the eCRF. AEs (any untoward medical occurrence in trial subject) do not necessarily have to have a causal relationship with treatment.

As a consistent method of collecting AEs, the subjects will be asked a non-leading question.

The investigator or delegates will record all directly observed AE, and all AE solicited or spontaneously reported by the subject, or reported in the subject's diary.

In addition to solicited AE following vaccination, unsolicited AE will be defined as follows: 1) AE, 2) serious AE (SAE), 3) medically significant event (condition prompting emergency room visit, physician visit not related to a common disease/not a routine visit or an SAE not related to a common disease), 4) investigator-determined new onset of chronic illness (NOCI). Any AE/SAE spontaneously reported at any study visit will be classified accordingly and reported in the eCRF.

AEs will be recorded in terms of medical diagnosis using the Medical Dictionary for Regulatory Activities (MedDRA). When this is not possible, the AE will be documented in terms of signs and symptoms observed by the investigator or as reported by the subject. In this case, each sign or symptom will be coded separately using MedDRA.

In addition, information provided for each AE will include: start date, treatment required if any assessment of the outcome at the time of reporting, causality, severity, and seriousness.

For each symptom the subject experiences, the subject will be asked if the subject received medical attention defined as hospitalization, or an otherwise unscheduled visit to or from medical personnel for any reason, including emergency room visits. This information will be recorded in the eCRF.

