- **Emergence during vaccination phase**: start date on or after the first date of injection of study vaccine or, adverse event increase in severity including to "serious" adverse event.

If an adverse event start date is equal to the first date of vaccination injection, missing or unknown, the adverse event will be considered as emergent.

When start and/or end dates of an adverse event are only partially known, adverse events will be categorized as emergent before, during (or after) vaccination phase using the following rules:

• If the partial end date is before (<) the first study vaccination (i.e., year or year & month is/are before the first study vaccination year or year & month) then the adverse event is emergent before vaccination phase.

Statistical Analysis Plan

If the partial start date is equal or after (≥) the first study vaccination (i.e., year or year & month is/are after or the same as the first study injection year or year & month) then the adverse event is emergent during vaccination phase.

The **maximum event severity** is the greatest severity associated with a preferred term for a reported adverse event according to the following order: Mild < Moderate < Severe < Potentially life threatening. Unknown/ Missing severity is considered as potentially life threatening.

Multiple AEs with the same PT for the same subject are counted only once.

Vaccination-related Adverse Events are those for which the cause has been evaluated by the investigator, and recorded either as very likely/certain, possibly related, probably related or unknown/missing.

Pre-Study, Concomitant and Post-Study Medications

A **pre-study medication** is a medication used only before the first study vaccination (i.e. medication end date < first study vaccination date).

A **post-study medication** is a medication used only after study termination (i.e. medication start date > study termination date). This will not be collected in the clinical database and will not be reported in the CSR.

All other medications are **concomitant**.

When start and/or end dates of a medication intake are missing, the medication is considered as concomitant with the study vaccination schedule.

If the first study vaccination date is missing then the medication is considered as concomitant with the study vaccination schedule, provided that the study vaccine was administered to the subject.

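### The severity scale for unsolicited AEs leaves two combinations without a grade, and separately the SAP counts every missing severity as potentially life threatening; both blur the descriptive severity tables.

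*Protocol*

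**What the plan says.** Protocol 7.1.6.1 gives one scale for unsolicited AEs: "These adverse event will be graded according to the severity scale in Table 1". Its four rows are:

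- Grade 1: "No interference with daily activity"
- Grade 2: "Some interference with daily activity but not requiring medical intervention"
- Grade 3: "Prevents daily activity and requires medical intervention"
- Grade 4: "Requiring Emergency Room (ER) visit or hospitalization"

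SAP 6.1.1 orders severity as "Mild < Moderate < Severe < Potentially life threatening" and adds: "Unknown/ Missing severity is considered as potentially life threatening". It counts multiple AEs with the same preferred term once per subject. SAP 6.3.14.3 tabulates unsolicited AEs by severity and takes the maximal severity when an AE recurs in a subject. Protocol 9.8.3 has the same maximal-severity rule but nothing on missing severity.

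Severity is one of the classifiers in the secondary safety endpoint (Protocol 3.3), and Protocol 9.8 presents all safety analyses by severity. Protocol 7.2.1 lists severity among the items provided for each AE. It also says that for each symptom "the subject will be asked if the subject received medical attention", which includes hospitalization and ER visits.

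**The concern.** A severity scale should place every event in exactly one row. Table 1 joins degree of interference and need for medical intervention in Grades 2 and 3, but uses interference alone in Grade 1 and place of care alone in Grade 4. Scales built this way tend to have gaps and overlaps. If sites resolve them differently, the line between Grade 2 and Grade 3 reflects site habit as well as the event.

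The SAP rule is a second and independent matter. Grade 4 in Table 1 has a factual criterion, an ER visit or hospitalization. An analysis rule that moves blanks into that row can fill it with events whose own eCRF record shows neither. The row is presumably small, and readers of a vaccine safety report look at it closely, so a few misplaced subjects would be noticed.

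**Working it through.** **Step 1: is Table 1 exhaustive and exclusive?** The inputs are the four row definitions. Cross interference (none, some, prevents) with medical intervention (no, yes) and ER visit or hospitalization (no, yes). Taking an ER visit or hospitalization to imply intervention leaves 3 × 3 = 9 combinations.

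| Interference | Intervention | ER visit or hospitalization | Grade(s) that fit |
|---|---|---|---|
| None | No | No | 1 |
| None | Yes | No | 1 |
| None | Yes | Yes | 1 and 4 |
| Some | No | No | 2 |
| Some | Yes | No | none |
| Some | Yes | Yes | 4 |
| Prevents | No | No | none |
| Prevents | Yes | No | 3 |
| Prevents | Yes | Yes | 3 and 4 |

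Five combinations have one grade, two have none and two have two. Of the six without an ER visit or hospitalization, two have no grade. Neither document gives a nearest-grade or highest-grade rule.

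**Step 2: compare with the protocol's other scale.** Appendix 3 grades solicited fatigue and myalgia 1 to 3 on interference alone. Fatigue that prevents activity and needs no treatment is therefore Grade 3 if solicited, and has no grade if unsolicited. SAP 6.3.14.3 combines solicited AEs that continue beyond Day 7 with the unsolicited ones, so the two scales can meet in one table.

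**Step 3: follow a blank through the SAP.** A missing severity, whatever its cause, is assigned to the top category (6.1.1). Suppose a subject has the same preferred term twice, once recorded as mild and once blank. The maximum is then potentially life threatening, and the recorded grade is lost from the table.

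**Step 4: size of the Grade 4 effect.** The documents give no rates, so these inputs are assumptions: 20% to 50% of subjects have an unsolicited AE, 5% to 20% of those have one in an ungraded combination, and 1% to 10% of these are left blank. Planned enrolment is 1,564, or 782 per arm (Protocol 9.1).

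False Grade 4 subjects = 1,564 × P(AE) × P(ungraded) × P(blank)

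- Lowest: 1,564 × 0.20 × 0.05 × 0.01 = 0.16 in total, about 0.1 per arm.
- Highest: 1,564 × 0.50 × 0.20 × 0.10 = 15.6 in total, about 7.8 per arm.

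This counts only blanks that arise in the two ungraded combinations, and assumes that those subjects would not otherwise be Grade 4. Blanks from other causes would add to it, at a rate the documents do not give.

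**The case against.** The strongest objection is that the two defects need not connect. A reader might infer that events without a row are left blank and so flow into Grade 4. The documents do not support that as the expected course. Protocol 7.2.1 asks for severity on each AE, 10.1 makes grading mandatory with review by the site investigator or designee, 10.2 describes eCRF checks for incomplete data, and Section 8 provides for monitoring. An event between two rows will most plausibly get one of the neighbouring grades. This objection stands: the main effect of the Table 1 gap is on Grades 2 and 3.

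A reader might also infer that the ungraded combinations are common, because the trial follows medically significant events to Day 336. No frequency is given. Medical attention in 7.2.1 means hospitalization or an otherwise unscheduled contact with medical personnel, whereas Table 1 speaks of intervention and does not define it. A physician visit without treatment may still be Grade 2.

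Nor can a multiple be put on the Grade 4 count. With 500 events, 1% truly Grade 4 and 2% blank, 5 becomes 15. With 0.1% blank, only 0.5 is added. The multiple is just the ratio of two chosen rates.

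Finally, the worst-case rule is pre-specified, applies to both arms and matches the treatment of missing causality in the same SAP section. Safety is descriptive, with no hypotheses (Protocol 9.8), and all AEs are listed. This limits the consequence but does not remove it. In a comparison of two arms, a worst-case assignment is not conservative in every direction, because blanks in the Engerix-B arm raise the comparator and can mask a difference.

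**Conclusion.** Two separate defects hold, both confined to the descriptive severity tables for unsolicited AEs.

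1. Table 1 is neither exhaustive nor exclusive. Two of the six combinations short of an ER visit or hospitalization have no grade, and two of all nine fit two grades. Grade 2 and 3 counts can therefore differ by site. This follows from the wording alone, apart from the assumption that an ER visit or hospitalization implies intervention.
2. The SAP does not separate missing severity from Grade 4, and the maximal-severity rule lets a blank displace a recorded grade. The Grade 4 row can then contain events with no ER visit or hospitalization. Blanks should be few, and the assumed range of about 0 to 8 subjects per arm reaches practically zero.

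The co-primary tests do not use severity. The graded stopping criteria in Protocol 7.8 refer to Appendices 3 and 4, and the SAP rule acts only at analysis. The changes are worth making because they are cheap, not because a false safety signal is likely.

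**What to change.** **Table 1.** Make the rows exhaustive, for example by grading 1 to 3 on interference alone, as Appendix 3 does for fatigue and myalgia. Keep Grade 4 and state that the highest applicable grade applies. The last part is needed because an ER visit without interference would otherwise still fit Grades 1 and 4. Under this rule all nine combinations have one grade, and the five that now have a single grade keep it. The exact wording is for the sponsor to settle. Medical attention is already recorded separately under Protocol 7.2.1, so that information is not lost.

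**SAP 6.1.1.** Show missing severity as its own row in the main tables, and keep the Grade 4 assignment as a worst-case sensitivity table.

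**Cost.** The Table 1 change needs a formal protocol amendment, matching eCRF help text, and a check of events already graded so that two grading rules are not mixed within the trial. The SAP change is one sentence before database lock and can be made alone if the protocol can no longer be amended.

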7.1.6.2 Solicited Adverse events

Reactions at the site of injection (redness/erythema, pain, tenderness, swelling/edema, pruritus), systemic reactions (nausea/vomiting, diarrhea, headache, fatigue, myalgia) and vital signs abnormalities (fever, tachycardia, bradycardia, hypertensions, hypotension, changes in respiratory rate) will be graded according to the FDA Guidance for Industry Toxicity Grading Scale for Healthy Adult and Adolescent Volunteers Enrolled in Preventive Vaccine Clinical Trials (2007) - see Appendix 3.

7.1.6.3 Laboratory tests abnormalities

Laboratory tests abnormalities will be graded according to the FDA Guidance for Industry Toxicity Grading Scale for Healthy Adult and Adolescent Volunteers Enrolled in Preventive Vaccine Clinical Trials (2007) - see Appendix 4.

7.1.7 Assessment of the outcomes

The investigator will assess the outcome of all AEs (including SAEs) recorded during the study as:

- Ongoing
- Recovered/resolved to pre-immunization health status
- Recovered/Resolved with sequelae
- Recovering/Improving
- Stabilized
- Unknown/Lost to Follow-up
- Fatal (SAE)

7.1.8 Causality

Relationship of all AE and SAE to the study interventions (causality) should be assessed by the investigator and the sponsor according to the criteria below:

- **Very likely/Certain:** A clinical event with a plausible time relationship to vaccine administration and which cannot be explained by concurrent disease or other drugs or chemicals.
- **Probable:** A clinical event with a reasonable time relationship to vaccine administration; and is unlikely to be attributed to concurrent disease or other drugs or chemicals.
- **Possible:** A clinical event with a reasonable time relationship to vaccine administration, but which could also be explained by concurrent disease or other drugs or chemicals.
- Unlikely: A clinical event whose time relationship to vaccine administration makes a causal
 connection improbable, but which could be plausibly explained by underlying disease or other
 drugs or chemicals.
- **Unrelated:** A clinical event with an incompatible time relationship and which could be explained by underlying disease or other drugs or chemicals.
- **Unclassifiable:** A clinical event with insufficient information to permit assessment and identification of the cause.

7.1.9 Unexpectedness

Adverse events and SAE will also be assessed according to the following categories:

• **Expected (anticipated):** the event is identified in nature, severity, and frequency in the investigator brochure or in the protocol.

• **Unexpected (unanticipated):** the event is not identified in nature, severity, or frequency in the investigator brochure or in the protocol.

7.1.10 Suspected adverse reaction

Suspected adverse reaction means any AE for which there is a reasonable possibility that the drug caused the AE. For the purposes of safety reporting, 'reasonable possibility' means there is evidence to suggest a causal relationship between the drug and the adverse event. A suspected adverse reaction implies a lesser degree of certainty about causality than adverse reaction, which means any adverse event caused by a drug.

7.2 Methods and timing for assessing, and recording safety parameters

Unless specified otherwise all AE occurring between obtaining the subject's written consent to participate in the study and subject's last study visit will be documented in the eCRF at all visits. All AE data and clinical laboratory data will be included in the study report.

Clinical investigators and ultimately the Site Principal Investigator have the primary responsibility for AE identification, documentation, grading, assignment of attribution and reporting to the sponsor.

7.2.1 AEs

All new AE or abnormal laboratory test values considered as clinically significant, expected or unexpected related or unrelated experienced after the subject received the study treatment should be recorded in the eCRF. AEs (any untoward medical occurrence in trial subject) do not necessarily have to have a causal relationship with treatment.

As a consistent method of collecting AEs, the subjects will be asked a non-leading question.

The investigator or delegates will record all directly observed AE, and all AE solicited or spontaneously reported by the subject, or reported in the subject's diary.

In addition to solicited AE following vaccination, unsolicited AE will be defined as follows: 1) AE, 2) serious AE (SAE), 3) medically significant event (condition prompting emergency room visit, physician visit not related to a common disease/not a routine visit or an SAE not related to a common disease), 4) investigator-determined new onset of chronic illness (NOCI). Any AE/SAE spontaneously reported at any study visit will be classified accordingly and reported in the eCRF.

AEs will be recorded in terms of medical diagnosis using the Medical Dictionary for Regulatory Activities (MedDRA). When this is not possible, the AE will be documented in terms of signs and symptoms observed by the investigator or as reported by the subject. In this case, each sign or symptom will be coded separately using MedDRA.

In addition, information provided for each AE will include: start date, treatment required if any assessment of the outcome at the time of reporting, causality, severity, and seriousness.

For each symptom the subject experiences, the subject will be asked if the subject received medical attention defined as hospitalization, or an otherwise unscheduled visit to or from medical personnel for any reason, including emergency room visits. This information will be recorded in the eCRF.

